2.2.2 Secondary Endpoints

- The AUC for RSV RNA viral load measured in nasopharyngeal swab samples by quantitative reverse transcription polymerase chain reaction (RT-qPCR)
- Percentage of subjects with RSV RNA viral load below the lower limit of quantitation in subjects receiving EDP-938 compared to placebo

- Plasma PK concentrations of EDP-938 and its major metabolites (EP-024636, EP-024594, and EP-024595)
- Safety endpoints include, but are not limited to, AEs, vital sign measurements, pulse oximetry measurements, and clinical laboratory test results (including chemistry, hematology, and urinalysis)
- Time to RSV RNA viral load below the lower limit of quantitation in subjects receiving EDP-938 compared to placebo
- RSV RNA viral load change from baseline

[REDACTED]

[REDACTED]

[REDACTED]

[REDACTED]

[REDACTED]

[REDACTED]

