11.6.2 Secondary Efficacy Analyses

Sensitivity analysis of the primary endpoint will be performed using the Markov Chain Monte Carlo (MCMC) method of multiple imputation (*Dong and Peng, 2013*). Following imputation using MCMC methods, the TSS AUC will be calculated and an ANCOVA model with treatment group and stratification factor as fixed effects, and the baseline TSS as a covariate will be performed. Treatment groups will be compared using a type III sum-of-squares. Other sensitivity analysis may include a mixed model repeated measures analysis on the change from Baseline over all visits.

The RSV RNA viral load AUC measured in nasopharyngeal swab samples by RT-qPCR will be measured on Days 1, 3, 5, 9, and 14. The trapezoid rule will be used to calculate the AUC of the RSV RNA viral load. An ANCOVA model with treatment group and stratification factor as fixed effects and the baseline RSV RNA viral load as a covariate will be performed. Treatment groups will be compared using a type III sum-of-squares. The proportion of subjects with RSV RNA below the lower limit of quantitation will be analyzed on Days 3, 5, 9, and 14. Treatment groups will be compared using a Cochran-Mantel-Haenszel test controlling for the stratification factor.

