#### 2.2.2 Secondary Endpoints

- AUC from Day 1 through Day 14 for RSV RNA viral load measured in nasopharyngeal swab samples by quantitative reverse transcription polymerase chain reaction (RT-qPCR)

- Percentage of subjects with RSV RNA viral load below the limit of detection on Days 3, 5, 9 and 14 respectively
- Plasma PK concentrations of EDP-938 and its major metabolites (EP-024636, EP-024594, and EP-024595) on Days 1, 3 and 5
- Safety endpoints include, but are not limited to, AEs, vital sign measurements, pulse oximetry measurements, and clinical laboratory test results (including chemistry, hematology, and urinalysis)
- Time to RSV RNA viral load below the limit of detection
- RSV RNA viral load and change from baseline over time

[REDACTED]

[REDACTED]

[REDACTED]

[REDACTED]

[REDACTED]

[REDACTED]

[REDACTED]

[REDACTED]

[REDACTED]

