Unless otherwise specified, the baseline is defined as the last non-missing assessment value for a subject, for that particular parameter, that is prior to or on the date of first dose of study drug. For subjects who are randomized, but not treated, the baseline will be defined as the last non-missing assessment prior to or on the date of randomization. Percent change from baseline will be calculated as the [change divided by baseline] multiplied by 100. In the event change=0, then the percent change will be 0. In the event baseline=0, then the percent change will be missing.

The date of first dose and the date of last dose will be the date collected on the End of Treatment eCRF.

For the reporting of this study both CDISC SDTM (SDTM Implementation Guide version 3.2) and ADaM (ADaM Implementation Guide version 1.1) standards will be applied. A subject will

be considered to have completed the study after his/her attendance at the last planned study visit (Day 14 ± 1 day), or the last unscheduled visit (if any occur), as applicable. For each subject his or her study completion status (Yes/No) is recorded on the End of Study CRF.

Summary Tables and Figures will be presented by treatment group. Tables and Figures values for treatment group will be labelled as follows: • “EDP-938 800mg” • “Placebo”. Models will include stratification factor for asthma/COPD status unless an insufficient amount of data exists where convergence or the analysis cannot be performed.

[REDACTED]

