The RSV type of each subject will be determined based on the final RSV value at baseline. If the baseline of RSV A is bigger, then the RSV type is A; otherwise, it is B. The analysis of the viral load will be based on the log scale of the RSV.

The RSV RNA viral load AUC will be derived similarly as described in *Section 3.14.1*. The AUC will be calculated based on all available assessments collected on Days 1/baseline, 3, 5, 9, and 14 and the actual date/time of each assessment will be used for the calculation. For the baseline viral load (Day 1), time is set as 0. For each assessment post first dose, the actual time in days is computed as difference between the date/time of the assessment and the date/time of the first dose. The AUC is also standardized to 14 days by multiplying  $14/t_{\text{last}}$  where  $t_{\text{last}}$  is the actual time in days of the last available assessment. Additionally, the AUC from Day 1 through Day 3, the AUC from Day 1 through Day 5, and the AUC from Day 1 through Day 9 will be also derived and standardized similarly as for AUC from Day 1 through Day 14.

An ANCOVA model with treatment group and asthma/COPD status (present or absent) as factors, and the baseline RSV RNA viral load as a covariate will be performed for the RSV RNA viral load AUC from Day 1 through Day 14. Treatment groups will be compared using a type III sum-of-squares. The least-squares means, standard errors and two-sided 95% confidence intervals (CI) will be presented for individual groups and the difference between groups. The same ANCOVA analysis will be performed for the AUC from Day 1 through Day 3, from Day 1 through Day 5, and from Day 1 through Day 9.

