The proportion of subjects with RSV RNA viral load below the limit of detection (LOD) will be analyzed on Days 1, 3, 5, 9, and 14, respectively. Treatment groups will be compared at each visit day using a Cochran-Mantel-Haenszel test controlling for the stratification factors of asthma/COPD status (present or absent). Additionally, the number and proportion of subjects with RSV RNA viral load below LOD will be summarized for each treatment group, and their respective 95% CIs will be reported based on the normal approximation. The adjusted difference in proportions between the 2 treatment groups will be computed as a weighted average of the treatment differences across strata using the Mantel-Haenszel weights, and the associated 95% CI will be provided using the Sato variance estimator (Sato, 1989).

[figure not shown]
Time to RSV RNA viral load below LOD will be analyzed using a Cox Proportional Hazards model. Stratification factors, baseline RSV RNA viral load and asthma/COPD status (present or absent), will be included. For calculating time to RSV viral load below LOD it is required of at

least two consecutive timepoints (or end of study) with viral load below LOD. Time to RSV viral load below LOD will be defined as the time between the date of first dose to the first date of achieving viral load below LOD, of the two consecutive timepoints or end of study. Subjects who discontinue early and subject who do not achieve viral load below LOD will be censored at the end of study date reported on the End of Study CRF. A Kaplan-Meier curve will display the probability estimates of achieving RSV RNA viral load below LOD. Descriptive statistics on the graph will include the median and 95% confidence interval at a minimum.

Descriptive statistics will be displayed for RSV RNA viral load and change from baseline by visit (Days 1, 3, 5, 9 and 14) and will include at a minimum the number of non-missing measurements, mean, standard deviation, median, minimum, 25th percentile, 75th percentile, maximum, and 95% CI for the mean.

Line graph of RSV RNA viral load will be produced:

- (1) Observed mean viral load  $\pm$  95% confidence interval by days (1, 3, 5, 9 and 14) for each treatment group

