### 3.17 Subgroup and Covariate Analyses

TSS AUC from Day 1 through Day 14 and RSV RNA viral load AUC from Day 1 through Day 14 will be analyzed by RSV type (A or B) using the same ANCOVA analysis as described in Section 3.14.1 and Section 3.14.2, except that RSV type and treatment by RSV type interaction are added to the model.

Other subgroup analyses may be explored as allowed by data.

[REDACTED]

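### Viral load change from baseline is a listed secondary endpoint, but the SAP plans no adjusted between-arm difference for it at any visit, Day 5 included

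*SAP*

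**What the plan says.** Protocol 2.2.2 lists "RSV RNA viral load change from baseline" as a secondary endpoint, and SAP 2.2.2 lists "RSV RNA viral load and change from baseline over time". Both sit under the secondary objective on antiviral efficacy.

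For this endpoint SAP 3.14.2 plans: "Descriptive statistics will be displayed for RSV RNA viral load and change from baseline by visit (Days 1, 3, 5, 9 and 14". The statistics named there are the count, mean, SD, median, quartiles, range and a 95% CI for the mean. A line graph shows the observed mean load with its CI "by days (1, 3, 5, 9 and 14) for each treatment group". SAP 3.1 sets the layout: "Summary Tables and Figures will be presented by treatment group".

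For the viral load AUC the same section does specify a model, an ANCOVA with treatment, asthma/COPD status and "the baseline RSV RNA viral load as a covariate will be performed for the RSV RNA viral load AUC". It reports a between-group difference with a 95% CI and is repeated for Days 1–3, 1–5 and 1–9.

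**The concern.** A listed efficacy endpoint would normally come with a stated estimate of the treatment difference. Here the reader gets two columns of arm-level summaries. The quantity most directly tied to a 5-day antiviral course, the Day 5 difference in log10 viral load, has no planned estimate.

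Two things are at stake. Arm-level CIs are a poor basis for comparing arms. Raw changes also carry any chance imbalance in baseline load, which the AUC model removes by adjustment.

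**Working it through.** **1. Is a between-arm method given anywhere in the visible text?** The viral load secondary endpoints compare as follows (SAP 3.14.2).

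| Endpoint | Between-arm analysis | Adjustment |
|---|---|---|
| AUC, Days 1–3, 1–5, 1–9, 1–14 | ANCOVA, difference and CI | baseline load, asthma/COPD |
| Proportion below limit of detection, by visit | Cochran-Mantel-Haenszel, weighted difference and CI | asthma/COPD |
| Time to below limit of detection | Cox model | baseline load, asthma/COPD |
| Change from baseline, by visit | none | none |

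Three other places could have filled the gap, and none does.
- Protocol 11.6.2 says "Other sensitivity analysis may include a mixed model repeated measures analysis on the change from Baseline over all visits", but this stands in the paragraph on sensitivity analyses of the primary symptom endpoint, and it is optional.
- Protocol 11.9 plans subgroup ANCOVA models on primary and secondary endpoints. These are interaction models, and SAP 3.17 narrows the viral load part to the AUC: "RSV RNA viral load AUC from Day 1 through Day 14 will be analyzed by RSV type (A or B". Other subgroup analyses are left as optional.
- Protocol 11.1 allows inference as appropriate, which names nothing for this endpoint.

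The conclusion covers visible text only. SAP 3.14.2 itself shows no redacted block.

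**2. Does the Day 1–5 AUC supply the Day 5 difference?** At nominal times of 0, 2 and 4 days after first dose (Days 1, 3, 5) the trapezoid rule gives

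AUC = 2(y0 + y2)/2 + 2(y2 + y4)/2 = y0 + 2y2 + y4.

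Dividing by 4 gives weights of 25% baseline, 50% Day 3 and 25% Day 5. For Days 1–14 (times 0, 2, 4, 8, 13) the weights are 1, 2, 3, 4.5 and 2.5, total 13, so Day 5 has 3/13 = 23%. Rescaling by a constant does not change these shares. A difference confined to Day 5 reaches the time-averaged Day 1–5 AUC at one quarter of its size.

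**3. What would a comparison of the two arm summaries carry?**
- With equal standard errors, two 95% CIs stop overlapping only when the difference exceeds 2 × 1.96 = 3.92 SE. A 5% test needs 1.96 × √2 = 2.77 SE. The ratio is 1.41. Non-overlap therefore demands a difference 41% larger, equivalent to z = 3.92/√2 = 2.77, or p of about 0.006.
- With 35 subjects per arm (protocol 5.6), the SE of the baseline mean difference is √(2/35) = 0.24 SD. With equal SDs at both times, an imbalance of that size moves the raw-change comparison by (1 − r) × 0.24 SD: 0.19 SD at r = 0.2 and 0.12 SD at r = 0.5.

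**4. How much precision does adjustment buy?** The documents give no SD or baseline-to-visit correlation for viral load, so r and the SD ratio are assumptions. With s0 and s1 the baseline and follow-up SDs, the variance ratio of adjusted to raw change is

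s1²(1 − r²) / (s0² + s1² − 2r·s0·s1).

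If s1 = s0 this is (1 + r)/2. If s1 = 2·s0 it is 4(1 − r²)/(5 − 4r).

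| r | Ratio, s1 = s0 | CI narrower by | Ratio, s1 = 2·s0 | CI narrower by |
|---|---|---|---|---|
| 0.2 | 0.60 | 23% | 3.84/4.2 = 0.914 | 4% |
| 0.3 | 0.65 | 19% | 3.64/3.8 = 0.958 | 2% |
| 0.5 | 0.75 | 13% | 3.00/3.0 = 1.000 | 0% |

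(CI narrowing = 1 − √ratio.) If the follow-up SD is below the baseline SD, the gain exceeds the equal-variance column.

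The plan states no power or effect size for this endpoint, so there is no figure to reproduce. The sample size rests on the symptom AUC and is unaffected.

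**The case against.** The strongest reply is that the plan is coherent as it stands. This is a Phase 2b trial of about 70 subjects, sized for the symptom AUC and with no multiplicity adjustment. It models the integrated viral load and clearance, and describes the visit profile. A reader might infer that the trial yields no treatment effect on viral load, or that the AUC only averages over the full 14 days. The documents do not support either. The Day 1–5 AUC covers the treatment period with baseline and stratum adjustment, and the proportion below the limit of detection is compared at each visit.

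A reader might also infer that no CI for a Day 5 difference can be had. That goes too far: the displayed n, mean and SD for each arm are enough to compute an unadjusted Welch interval. That readers will in fact judge by overlapping CIs is conjecture.

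A further objection is that SAP 3.14.2 sets undetected values to zero on the log scale. A normal-theory model may then fit poorly once many subjects have cleared virus.

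All of this stands and limits the point. It does not remove it. The SAP calls its safety methods primarily descriptive but says nothing similar for this efficacy endpoint, and none of the planned comparisons estimates the visit-level difference.

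**Conclusion.** The point holds as a cheap improvement in the analysis of one endpoint. What is missing is a pre-specified, baseline- and stratum-adjusted difference in change of log10 viral load at each visit.

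That finding rests on the text alone. The size of the benefit rests on assumptions. The 13–23% gain should not be read as a measured loss: it compares adjusted change with a raw-change contrast that the SAP does not plan, and it falls to 0–4% if variability doubles after baseline. Protection against chance baseline imbalance is a separate benefit. Its stated size also assumes r and equal SDs.

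**What to change.** In SAP 3.14.2, apply the existing ANCOVA (treatment, asthma/COPD status, baseline log10 viral load) to change in log10 viral load at Days 3, 5, 9 and 14. Alternatively, fit one repeated-measures model with treatment, visit, treatment-by-visit, baseline, baseline-by-visit and asthma/COPD status, using the visit-wise ANCOVA if it does not converge. Report the least-squares mean difference and 95% CI at each visit, highlight Day 5, and state that no multiplicity-controlled claim attaches to these estimates. Keep the descriptive table and graph.

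The cost is SAP wording settled before unblinding, as protocol 11.1 requires, and one model on data already collected. No subjects or samples are added. The downsides are a few more nominal comparisons and a need to read Days 9 and 14 cautiously, because undetected values sit at zero on the log scale. The SAP should say so beside the results.

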### 3.15 Safety Analyses

Statistical methods for the safety analyses will be primarily descriptive in nature. The SAF will be used for all analyses, unless stated otherwise.

#### 3.15.1 Adverse Events

Adverse events will be summarized by the Medical Dictionary for Regulatory Activities (MedDRA) using the system organ class (SOC) and preferred term (PT) by treatment group. All subjects in the SAF Population will be included in the summaries. AEs will be classified as pre-treatment AEs and treatment emergent adverse events (TEAEs) and are defined as follows:

- Pre-treatment AE: A pre-treatment event is any event that meets the criteria for an AE/SAE and occurs after the subject signs the ICF but before receiving the first administration of study drug.
- TEAE: A TEAE is defined as an AE occurring or worsening on or after the first dose of study drug.
- Treatment-Related AEs: AE will be defined as related if causality is related or possibly related. AEs where the causality is missing will be assumed to be related.
- Grade AEs: Grade AEs (serious and non-serious) in accordance with the NCI/CTCAE scale as follows: Mild (Grade 1), Moderate (Grade 2), Severe (Grade 3), Life-threatening (Grade 4), Death (Grade 5).

Where a subject has the same adverse event, based on preferred terminology, reported multiple times, the subject will only be counted once at the preferred terminology level in adverse event frequency tables. Where a subject has multiple adverse events within the same system organ class, the subject will only be counted once at the system organ class level in adverse event frequency tables. When reporting adverse events by severity, in addition to providing a summary table based on the event selection criteria detailed above, summary table will also be provided based on the most severe event - independent of relationship to study treatment.

Summaries of AEs will include the following at a minimum:

- Overall summary of AEs with a line for each of the following categories
- TEAEs
  - By PT and SOC
  - By PT
  - By SOC
- Study Drug-Related TEAEs - by PT and SOC
- TEAEs of Grade 3 or Higher - by PT and SOC
- TEAEs by Maximum Grade – by PT and SOC

- TEAEs leading to study drug discontinuation – by PT and SOC
- AEs leading to death – by PT and SOC
- Serious TEAEs – by PT and SOC
- Study Drug-Related Serious TEAEs – by PT and SOC

### 3.15.2 Clinical Laboratory Data

Laboratory assessments will be reported as the mean of observed and change from baseline across scheduled visits, and as the incidence rate of shift change from baseline. Shift from baseline tables will be generated for each treatment group for selected analytes. Laboratory shifts will be displayed as treatment-emergent abnormal, high, or low results. The following details the summary types where LLN = lower limit of normal and ULN = upper limit of normal.

For categorical tests: Treatment-emergent abnormal is defined as a change from normal at baseline to abnormal at any post-baseline visit.

For continuous tests:

- Treatment-emergent high is defined as a change from a result less than or equal to the high limit at baseline to a value greater than the high limit at any time post-baseline.

For all parameters except Glomerular Filtration Rate (GFR) results will be reported according to any value greater than the high limit, any value greater than  $2 \times$  ULN and  $3 \times$  ULN.

- Treatment-emergent low is defined as a change from a result greater than or equal to the low limit at baseline to a value less than the low limit at any time post-baseline.

Results for GFR will be reported according to any value less than  $(\frac{1}{2}) \times$  LLN and  $(\frac{1}{4}) \times$  LLN. All other results will be reported to any value less than the lower limit.

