3.2 Subject Exclusion Criteria

Subjects will not be eligible to participate in the study if they meet any of the following criteria:

1. Clinical evidence of a lower respiratory tract infection, as determined by the Investigator.
2. Anticipated need for hospitalization or emergency room care within 24 hours of Screening.
3. Receipt of systemic antiviral, antibacterial, antifungal, or antimycobacterial therapy within 7 days of Screening and for the duration of the study.
4. Awareness of concomitant respiratory infections that are viral (other than RSV), bacterial, or fungal, including systemic bacterial or fungal infections, within 7 days of Screening.
5. Severe acute respiratory syndrome coronavirus 2 (SARS-CoV-2) positive within 28 days of Screening or at Screening following signature of full ICF.
6. Frailty scale score ≥ 4 at Screening.
7. History of chronic liver disease (eg, hemochromatosis, Wilson's disease, alpha-1 antitrypsin deficiency, autoimmune hepatitis, nonalcoholic steatohepatitis, and/or alcoholic liver disease); a history of biliary disease (eg, primary sclerosing cholangitis, cholecystitis, choledocholithiasis); or a history of portal hypertension. A diagnosis of hepatic steatosis (fatty liver) is not exclusionary.
8. Heart disease: any congenital heart disease, acute or chronic heart failure, ischemic heart disease, congenital long QT syndrome, or any clinical manifestation resulting in QT interval prolongation. Note: Subjects with controlled hypertension without cardiac compromise will be allowed to enroll. See exclusion criterion #18 for prohibited medications.
9. Neurological and neurodevelopmental disorders (including disorders of the brain, spinal cord, peripheral nerve, and muscle, eg, cerebral palsy, epilepsy [seizure disorders], stroke, muscular dystrophy, or spinal cord injury). Note: Minor neurological disorders (eg, past concussions, headaches, migraine) are allowed.
10. Malignant tumor or history of malignancy that may interfere with the aims of the study or a subject completing the study.
11. Prior receipt or the subject is waiting to receive a bone marrow, stem cell, or solid organ transplantation.
12. Diagnosis of cystic fibrosis.
13. Known positive human immunodeficiency virus, active hepatitis A virus infection, chronic hepatitis B virus infection, and/or current or treated hepatitis C virus infection.

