11.7.3 Clinical Laboratory Data

Laboratory assessments will be reported as mean change from Baseline across scheduled visits, and as the incidence rate of shift change from Baseline. Shift from Baseline tables will be generated for each treatment group for selected analytes. Laboratory shifts will be displayed as treatment-emergent abnormal, high, or low results. The following details the summary types where LLN = lower limit of normal and ULN = upper limit of normal.

For categorical tests: Treatment-emergent abnormal is defined as a change from normal at Baseline to abnormal at any post-Baseline visit.

For continuous tests:

- Treatment-emergent high is defined as a change from a result less than or equal to the high limit at Baseline to a value greater than the high limit at any time post-Baseline.
Results will be reported according to any value greater than the high limit, any value greater than $2 \times$ ULN and $3 \times$ ULN.
- Treatment-emergent low is defined as a change from a result greater than or equal to the low limit at Baseline to a value less than the low limit at any time post-Baseline.
Results will be reported to any value less than the lower limit, any value less than $2 \times$ LLN and $3 \times$ LLN.

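### Worsening from an already abnormal baseline is missing from the laboratory treatment-emergent incidence, and GFR has no row below LLN

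*SAP*

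**What the plan says.** SAP 3.15.2 sets three rules for the laboratory incidence summary.

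- High, continuous tests: "Treatment-emergent high is defined as a change from a result less than or equal to the high limit at baseline" to a value above it at any later time.
- Low, continuous tests: "Treatment-emergent low is defined as a change from a result greater than or equal to the low limit at baseline" to a value below it later.
- Categorical tests: "Treatment-emergent abnormal is defined as a change from normal at baseline to abnormal at any post-baseline visit".

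Protocol 11.7.3 has the same definitions; for high it reads "Treatment-emergent high is defined as a change from a result less than or equal to the high limit at Baseline".

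Thresholds follow. On the high side, "For all parameters except Glomerular Filtration Rate (GFR) results will be reported according to any value greater than the high limit", and also above 2 x and 3 x ULN. On the low side, "Results for GFR will be reported according to any value less than" 1/2 x LLN and 1/4 x LLN, while all other tests are reported below LLN. Protocol 11.7.3 has no GFR exception: it reports below LLN for every test, and adds rows below 2 x and 3 x LLN.

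SAP 3.15.2 also provides mean observed values and mean change from baseline by visit, and shift tables for selected analytes that it does not name. Shifts are to be shown as treatment-emergent abnormal, high or low. For adverse events, SAP 3.15.1 says "A TEAE is defined as an AE occurring or worsening on or after the first dose of study drug".

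**The concern.** Clinical laboratory results are a listed safety endpoint (SAP 2.2.2), and the incidence table is the main by-arm view of individual outliers. As defined, it records a crossing of the limit, not a deterioration. Adverse events in the same SAP count worsening; laboratory values do not.

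Abnormal baselines are plausible. The eligibility criteria set no numeric chemistry or haematology limit, and laboratory findings exclude a subject only through the investigator's opinion (Protocol 3.2, criterion 23). The Day 1 panels are drawn in randomized subjects (Schedule of Assessments). BMI up to 40 kg/m² is allowed, and "A diagnosis of hepatic steatosis (fatty liver) is not exclusionary".

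The GFR rule raises a separate problem. A value can meet the SAP's own definition of treatment-emergent low and still fit neither GFR row. It is also unclear which variable is meant: Protocol 8.4.1 and Table 2 provide Cockcroft-Gault estimated creatinine clearance and do not name GFR.

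**Working it through.** The plan gives no figure for the laboratory summaries, so there is none to reproduce. The check applies the SAP 3.15.2 rules to hypothetical baseline and post-baseline pairs.

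**High side, in multiples of ULN.** Rule: baseline ≤ 1 and post-baseline > 1.

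| Baseline → later | Treatment-emergent high? | Exceeds 2x / 3x ULN? |
|---|---|---|
| 0.9 → 1.1 | yes | no / no |
| 1.0 → 3.5 | yes | yes / yes |
| 1.1 → 3.5 | no | yes / yes |
| 1.5 → 4.5 | no | yes / yes |
| 2.5 → 3.2 | no | yes / yes |

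The last three rows would appear in the >2x and >3x ULN lines only if those lines cover all subjects. The SAP does not settle this: the lines speak of any value, but they sit beneath the treatment-emergent definition.

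**GFR, in multiples of LLN.** Rule for low: baseline ≥ 1 and post-baseline < 1. Reporting rows: < 0.5 and < 0.25. Fall = 1 − later/baseline.

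| Baseline → later | Fall | Treatment-emergent low? | GFR row |
|---|---|---|---|
| 1.2 → 0.95 | 21% | yes | none |
| 1.2 → 0.6 | 50% | yes | none |
| 1.0 → 0.5 | 50% | yes | none |
| 1.2 → 0.49 | 59% | yes | <1/2 |
| 0.9 → 0.4 | 56% | no | <1/2, if the row covers all subjects |

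The band with no threshold row runs from 1/2 x LLN up to LLN. The documents give no LLN. If it were 60 mL/min the band would be 30 to 60; if 90 mL/min, 45 to 90. Both are assumptions.

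**How many subjects.** About 35 per arm (SAP 3.4). The proportion p beyond a limit at baseline is not in the documents and is assumed. Expected number = 35p; chance of at least one = 1 − (1 − p)^35.

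- p = 5%: 1.75 subjects; 83%
- p = 10%: 3.5 subjects; 97%
- p = 20%: 7 subjects; more than 99%

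These are subjects who could not be counted for that analyte and direction, not subjects who worsen.

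**How visible one case is in the mean.** One subject of 35 rising from 1.5 to 4.5 x ULN moves the arm's mean change by (4.5 − 1.5)/35 = 0.086 x ULN.

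**The case against.** The strongest reply is that nothing is lost from the safety endpoint. The endpoint is clinical laboratory results in general. Mean change is not conditional on baseline status, all data are listed with out-of-range values flagged (Protocol 11.7), clinically significant findings are recorded as adverse events (Protocol 8.4), and treatment-emergent adverse events include worsening. Serum creatinine, which has the high-side rows, may show a renal decline as well. This stands: a reader might infer that such worsening disappears from the safety reporting, and the documents do not support that. These routes are weaker for comparing arms, however. A mean hides one outlier, listings are not tabulated by arm, and adverse event capture rests on the investigator's judgement.

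Three other strong readings also fail.

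- That a subject going from 1.5 to 4.5 x ULN appears in no category. The threshold lines may cover all subjects, and the table shells are in a separate document (SAP 3.1).
- That affected subjects dilute the incidence by staying in the denominator. The Safety Population is the default for safety analyses (SAP 3.15), but 3.15.2 does not say whether the incidence is restricted to subjects able to have the event.
- That the rule requires a fully normal baseline. That is exact only for categorical tests; a subject below LLN can still become treatment-emergent high.

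It is also fair to say that the population is screened: chronic liver disease, biliary disease and known or suspected renal disease are excluded (Protocol 3.2), so the share with abnormal baselines may be small for some analytes. Finally, the safety analysis is primarily descriptive, and no test or efficacy result is affected.

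**Conclusion.** The point holds as a gap in one table. Same-direction worsening from an abnormal baseline does not enter the treatment-emergent incidence under either document. That follows from the wording and needs no assumption. The scope of the >2x and >3x ULN rows and the denominator are undetermined, so two programmers could produce different tables from the same text.

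The GFR point is also firm: the SAP drops a row that the protocol applies to every test, and gives no reason in 3.15.2. The protocol's rows below 2 x and 3 x LLN would take in values inside the normal range, so leaving those out is sensible, but it does not explain the loss of the <LLN row. The mismatch between GFR and estimated creatinine clearance needs reconciling.

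The number of subjects affected cannot be derived from the documents. About 2 to 7 of 35 per arm per analyte rests wholly on the assumed 5% to 20%. This is an inexpensive improvement to a descriptive safety summary, not a flaw that invalidates it.

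**What to change.** In SAP 3.15.2:

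1. Define treatment-emergent as a post-baseline category worse than the baseline category. High: ≤ULN, >ULN, >2x ULN, >3x ULN. Low: ≥LLN, <LLN, with <1/2 and <1/4 LLN added for renal function. Alternatively, keep the present definition and add tables of baseline category by worst post-baseline category.
2. State that the >2x and >3x ULN rows include all subjects whatever their baseline, and state the denominator for each incidence.
3. Restore the <LLN row for renal function, and name the variable collected, Cockcroft-Gault estimated creatinine clearance, or say how GFR is derived.

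Under the first option all three uncounted high-side examples above would be counted, and the falls to 0.95, 0.6 and 0.5 x LLN would have a row. Some worsening would still be missed: movement within a category, such as 1.1 to 1.9 x ULN, and further falls in non-renal tests already below LLN.

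The cost is SAP wording and a little table programming, before unblinding. The downside is a slightly higher reported incidence of laboratory shifts. No data collection changes.
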